#### 6.4.5. Main outcome

Non responders will be those patients not achieving a reduction in HBI of at least 2 points from baseline for CD, and a decrease in the PMS of at least 2 points for UC.. In the cases where these indexes are not available, clinical response will be evaluated according to physician criteria at short term (10 weeks after starting the anti-TNF) and at long term (at least 6 months after starting the anti-TNF). Primary non-responders (PNR) were defined as patients with no clinical response at short term. Loss of response (LOR) was defined as loss of the effect of the drug along the follow up in a patient with initial response.

Reasons to stop the drug will be classified as follows: PNR, LOR, side effects (SE), remission and other.

## 7. Statistical Analysis

### 7.1. Sample size calculation

Response to treatment with biologics is estimated at 50%, meaning that half of included patients are expected to be non-responders. Considering a minimal sample of 10 patients that present the event of interest per independent variable included in the logistic regression model and a maximum of 10 independent variables per model, a minimum estimated sample of 200 UC patients and 200 CD patients is required.

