In the recent years, the aim of IBD treatment has evolved from symptomatic control to deep remission, which is defined as the absence of symptoms, markers of inflammatory activity, and endoscopic lesions, and is associated with fewer admissions to hospital, surgeries and better HRQoL. Main current treatment modalities for UC and CD include 5-aminosalicylates, corticosteroids, immunomodulators (including thiopurines, methotrexate, tacrolimus, cyclosporine, and biological therapies), and surgery. Conventional treatment with corticosteroids and immunomodulators has not been able to reduce the complications of the disease or modify its course. Over the last decade, biologic treatments, such as infliximab, adalimumab, certolizumab pegol, golimumab and vedolizumab has been used in patients with moderate to severe CD, and in those with acute severe UC who failed to respond to corticosteroids.

At present, early introduction of immunomodulators and biologic agents in patients with more serious disease is probably the most widely accepted management strategy. Treatment of IBD with anti-TNF $\alpha$  since IBD diagnosis, albeit capable of inducing and maintaining mucosal healing and reducing surgery and hospitalization rates, may imply overtreatment of patients with milder forms of disease, thus emphasizing the need for accurate prognostic markers to guide patient selection. It is worth mentioning that although anti-TNF $\alpha$  therapy is thought to be an effective approach for IBD, up to 30% of patients do not respond to induction therapy (primary non-response) and a significant proportion loses response over time (secondary non-response). Very often patients profile in randomized controlled trials is quite restrictive and not representative of patients routinely treated under usual clinical conditions, especially, in terms of presence co-morbidities, concomitant treatments and previous use of biologics.

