#### **7.4. Assessment of the primary objective: Evaluate the impact of the co-morbidities profile in IBD patients on treatment response to biological therapy**

In order to determine the level of correlation between the co-morbidities profile and treatment response, adjusting for sociodemographic and clinical profile of patients, two logistic regression models will be conducted. The dependent variable of the models will be the lack of response during the induction phase (primary non response) and the loss of response during the maintenance phase (secondary loss of response) (see section 6.4.6). In both models independent variables will include all comorbidities included in the study, as well as sociodemographic and clinical variables as covariates. The maximum number of independent variables included in the model will be defined according to the number of patients per response category in the dependent variable. The maximum number of variables will be defined to ensure a minimum of 10 patients per independent variable and response category in the dependent one.

Depending on the volume of patients that have discontinued a biological treatment and started treatment with a different biologic during the reference period, this sample may be separately analyzed.

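### Protocol 7.1 uses one 50% non-response rate for two models with different events and denominators, so the stated capacity of 10 variables per model is not shown

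*Protocol*

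**What the plan says.** Protocol section 7.1 takes one rate for everyone enrolled: "Response to treatment with biologics is estimated at 50%, meaning that half of included patients are expected to be non-responders". It then sets the rule, "Considering a minimal sample of 10 patients that present the event of interest per independent variable included in the logistic regression model", allows "a maximum of 10 independent variables per model", and concludes that "a minimum estimated sample of 200 UC patients and 200 CD patients is required".

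Protocol section 7.4 plans two logistic models, one for primary non-response during induction and one for loss of response during maintenance. Its rule is stricter than that of section 7.1, because it applies to both outcome groups: the number of variables must "ensure a minimum of 10 patients per independent variable and response category in the dependent one".

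Protocol section 6.4.5 fixes who can enter the second model: "Loss of response (LOR) was defined as loss of the effect of the drug along the follow up in a patient with initial response".

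The only rate for either outcome is in Protocol section 4, which says of anti-TNF therapy that "up to 30% of patients do not respond to induction therapy (primary non-response". The same sentence says that a significant proportion later lose response, without a figure.

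SAP section 7.2 keeps two models, lists disease (CD or UC) among the candidate variables, and compares maintained response with loss of response. SAP Appendix 1 has one regression table per outcome (14.3.1.2 and 14.3.1.4).

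**The concern.** The sizing treats the two models as if each had all included patients and half of them with the event. Primary non-response has all starters as its denominator, and the one figure given for it is a ceiling below 50%. Loss of response has only initial responders as its denominator, so every primary non-responder counted as an event in the first model is lost to the second. A single overall rate cannot describe both.

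What is at stake is the justification of the sample size. A reader of section 7.1 would take it that 200 + 200 supports up to 10 variables in each model. The SAP starts from 29 candidate variables, 19 of them comorbidities, and selects by univariable p<0.1 and stepwise methods. SAP section 7.2 does not repeat the section 7.4 cap. The true capacity of each model therefore matters for how many comorbidities can be examined with adjustment.

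**Working it through.** **Inputs.** N = 200 per disease, or 400 pooled; 10 per variable; maximum 10 variables; 50% non-response (Protocol 7.1). The rule applies to each response category (Protocol 7.4). Primary non-response (PNR) of 30% is an assumption, borrowed from the upper figure in Protocol 4. Loss of response (LOR) is among initial responders (Protocol 6.4.5). The documents give no LOR rate, so 20% to 60% is shown as an assumption. All enrolled patients are taken to have both outcomes classified where they apply.

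**Formula.** Variables supported = smaller response category / 10, rounded down. For PNR the categories are N × PNR and N × (1 − PNR). For LOR the base is R = N × (1 − PNR), and the categories are R × LOR and R × (1 − LOR).

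**1. The plan's figure.** 10 × 10 = 100 events; 100 / 0.50 = 200. This reproduces exactly. The section 7.4 rule gives the same for one model with a 50/50 split: 100 / 10 = 10 variables.

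**2. Per disease, any rates.** Ten variables for PNR need at least 100 primary non-responders. Ten for LOR need 100 + 100 = 200 initial responders. The groups do not overlap, so 300 patients are needed against 200 planned. In general, k variables in both models need 10k + 20k = 30k patients, and 200 / 30 = 6.7, so the best common value is 6. Under the events-only rule of section 7.1, just one split works: 100 primary non-responders, with all 100 responders losing response. That leaves no comparison group.

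**3. Per disease, with rates.** At 30% PNR there are 60 events, so 6 variables, and 140 responders remain. At 50% PNR the first model reaches 10, but 100 responders remain and the second supports at most 5 (50/50 split).

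**4. Pooled (N = 400), 30% PNR.** 120 events give 12 variables; 280 responders remain.

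| Assumed LOR | Per disease (140): smaller group, variables | Pooled (280): smaller group, variables |
|---|---|---|
| 20% | 28, 2 | 56, 5 |
| 30% | 42, 4 | 84, 8 |
| 36% | 50.4, 5 | 100.8, 10 |
| 40% | 56, 5 | 112, 11 |
| 50% | 70, 7 | 140, 14 |
| 60% | 56, 5 | 112, 11 |

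Ten pooled LOR variables require LOR between 100 / 280 = 35.7% and 180 / 280 = 64.3%. Because 30% is a ceiling, lower PNR should be considered too: at 20%, the pooled PNR model has 80 events, so 8 variables.

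**5. Pooled, 50% read as overall non-response.** Total non-responders are 400 × 0.50 = 200, shared between the models. At 30% PNR, 120 are used and 200 − 120 = 80 remain for LOR: 12 and 8 variables. At 20% PNR the counts are 80 and 120: 8 and 12. Both models reach 10 only when the 200 split as 100 and 100, that is, at exactly 25% PNR.

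**6. Pooled, 50% read as the rate for each outcome.** PNR: 200 events, 20 variables. LOR: 200 responders, 100 / 100, exactly 10 variables.

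**The case against.** The strongest reply is that the models are pooled. Both documents speak of two models, disease is a candidate covariate, and each outcome has one regression table. The SAP's statements that CD and UC are described separately sit in its descriptive sections (5 and 6) and in the prevalence endpoint. This stands. A reader might infer that the planned sample cannot support 10 variables in both models at all; the documents do not support that, because steps 4 and 6 show pooled scenarios that reach it. Pooling does not vindicate section 7.1, however: its calculation yields 200 per model, and asking for 200 of each disease follows from it only if models are fitted per disease.

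Second, a reader might infer that 50% contradicts 30%, or that the arithmetic is wrong. Neither follows. The 30% is a literature ceiling for anti-TNF, not a rate under this study's 2-point or physician-judged definition, and 50% may include later loss of response. The product and division are correct. The gap is that the 50% is not tied to an outcome or denominator.

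Third, the operational definition of loss of response in SAP section 7.1 does not restrict it to initial responders. Taken literally over all patients at 50%, 200 per disease would reach 10. But Protocol 6.4.5 restricts it, and the comparison in SAP section 7.2 and table 14.3.1.3, maintained primary response against loss of response, presupposes an initial response.

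Fourth, Protocol 7.4 lets the number of variables fall to fit the observed counts, 10 is a maximum, and 200 + 200 is a minimum. This stands and limits the harm: the result is fewer variables, not an analysis that cannot be run.

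**Conclusion.** The point holds in conditional form. For disease-specific models, 10 variables in both is unattainable at 200 under the section 7.4 rule, with no rate assumed; the best common number is 6. At an assumed 30% primary non-response, the limits are 6 for primary non-response and at most 7 for loss of response.

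For the pooled models in the SAP, 10 in both is attainable but not shown. At 30% primary non-response, it needs about 36% to 64% of responders to lose response; if 50% is overall non-response, the second model supports 8. These pooled results rest on the assumed 30%, on loss-of-response rates that the documents do not supply, and on complete outcome classification.

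The defect lies in the stated justification of the sample size and should be corrected. It is not a reason to enlarge the study.

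**What to change.** Keep 200 UC and 200 CD.

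- Restate Protocol section 7.1 for the pooled models that the SAP fits, with a separate assumed rate and denominator for each: primary non-response in all starters, loss of response in initial responders.
- Replace the blanket maximum of 10 with a limit for each model equal to the smaller response category divided by 10, shown over a range of rates. For example: 12 for primary non-response at 30%; for loss of response among the resulting 280 responders, 5 at 20%, 8 at 30%, and 10 or more from about 36% to 64%.
- Carry the section 7.4 cap, "a minimum of 10 patients per independent variable and response category in the dependent one", into SAP section 7.2, so that it binds the screening and stepwise selection.
- If disease-specific models are intended, say so and state the lower limits per disease.

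The cost is wording in both documents and no extra patients. The downside is that the stated number of variables becomes less favourable.

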### 7.2. Analysis population

All patients participating in the study that fulfill inclusion criteria, not presenting a major deviation of the study protocol will be included in the analysis.

### 7.3. General statistical analysis considerations

This section describes the main analyses that will be performed. Further information about detailed analyses, the methods of handling missing data, analysis methods and a list of table shells will be documented in a Statistical Analysis Plan (SAP) that will be

agreed with Takeda. All data analyses will be performed using SAS statistics software version 9.1 (SAS Institute Inc., Cary, NC) or SPSS for Windows version 19. All analyses will be performed in a manner consistent with the Strengthening the Reporting of Observational Studies in Epidemiology (STROBE) guidelines and applicable sections of the Consolidated Standards of Reporting Trials (CONSORT) guidelines.

All analyses will be primarily performed by descriptive statistical methods.

Continuous variables will be described with number of patients with valid / missing observations, mean, standard deviation, median, minimum and maximum. Additional descriptive statistics may be calculated as needed (e.g. quartiles other than the median, coefficient of variation, etc.). In particular, for non-normally distributed data, the median and interquartile range will be calculated. Categorical variables will be described by frequencies and related percentages per class level. Summaries will be reported overall.

In addition to descriptive analysis, many of the endpoints will undergo statistical testing to provide inferential summaries of subgroup comparisons (i.e. p-values, confidence limits).

Inter-individual comparisons will be performed: 2 sample t-test, Mann-Whitney test, ANOVA or Kruskall-Wallis test will be used to compare quantitative variables between study groups or categories or categorical variables; chi-square test or the exact Fisher test will be used to compare categorical variables between them.

#### **7.4. Assessment of the primary objective: Evaluate the impact of the co-morbidities profile in IBD patients on treatment response to biological therapy**

In order to determine the level of correlation between the co-morbidities profile and treatment response, adjusting for sociodemographic and clinical profile of patients, two logistic regression models will be conducted. The dependent variable of the models will be the lack of response during the induction phase (primary non response) and the loss of response during the maintenance phase (secondary loss of response) (see section 6.4.6). In both models independent variables will include all comorbidities included in the study, as well as sociodemographic and clinical variables as covariates. The maximum number of independent variables included in the model will be defined according to the number of patients per response category in the dependent variable. The maximum number of variables will be defined to ensure a minimum of 10 patients per independent variable and response category in the dependent one.

Depending on the volume of patients that have discontinued a biological treatment and started treatment with a different biologic during the reference period, this sample may be separately analyzed.

## **7.5. Percentage of IBD patients exhibiting co-morbidities**

The number, percentage, and 95% confidence interval of IBD patients with each co-morbidity will be described.

## **7.6. Co-morbidities profile according to the level of IBD severity**

The percentage of patients reporting each co-morbidity at treatment initiation will be compared according to the IBD severity assessed using the PMS and the general disease activity for UC patients and the HBI and the general disease activity for CD patients. Multivariable regression models will be used to assess the relationship between the co-morbidities profile and the level of IBD severity.

# **8. Data management**

Patients' data will be collected through an eCRF specially designed for this study. The eCRF will constitute the analysis data source and will consist of a web application accessible from any computer with internet access. The SSL (128 bites) protocol will be used for web communication, ensuring confidentiality for all communication between servers and investigators computers by encrypting all data sent (safe connection).

Each investigator will have a user name and password to guarantee that data is not accessible to anyone else. Each investigator or designated person will be responsible for registering and verifying accuracy of patients' data introduced in the eCRF. By signing this protocol, investigators accept their digital signature to be legally equivalent and binding to its written form. When introducing their digital signature, investigators confirm all data has been reviewed and is considered accurate.

All data recorded by investigators will be reviewed by CRO personnel to detect missing information and data inconsistencies and indicate the corresponding queries in the monitoring reports. If any inconsistency is detected and resolved before locking the database, corrections will be included in the database.

Once the field work has been completed data collected will be validated for quality control and the statistical analysis of the results will be performed by the CRO.

The eCRF will allow defining filters in collected variables in order to avoid mistakes, as well as to obtain statistics about the main outcomes in real time. The eCRF will include specific logic checks and filters for collected variables in an effort to minimize errors in data entry. The eCRF will also allow the study team to obtain statistics on recruitment and eCRF completion progression in 'real-time'. The web application will be developed with the following technology:

- ASP.NET 2.0
- RDBMS My SQL v.5.0
- IIS 6.0
- SSL (128bits) validated by Verisign
- WEB server O.S. Windows 2003

The SSL technology implemented guarantees that all data transferred to the CRO database server will be encrypted and protected from external attacks. An audit trail process will ensure control of every movement made to the data stored. Information registered for every value stored in the database includes: the event date, responsible party, variable, old value, new value, and the type of action taken (creation, updating or deleting). This audit process provides an additional security mechanism for stored data and may also be useful in answering data entry questions by site personnel.

The two questionnaires to be filled in by patients during the study visit will be sent to investigators together with all the study documents. Investigators will have to send all questionnaires completed by included patients at their site to the CRO.

## 9. Practical considerations

### 9.1. Electronic case report form

An eCRF will be specifically designed for the present study and will include all the study variables required to meet the primary and secondary objectives of the study. The eCRF will consist of a web application accessible from any computer with internet access. Each investigator will have a unique access code to introduce patients' information in the eCRF.

Each patient will be assigned a 4-digit code: the two first digits will correspond to the site in which the patient has been recruited and the two last digits will be consecutively assigned after patient's inclusion in the study.

### 9.2. Monitoring and quality of data

On-site monitoring will not be conducted in the context of this study. Regular fortnightly phone calls will be made by study monitors in order to check inclusion status, solve any potential recruitment issues, check data plausibility etc. Investigators will receive all documents before the study begins. The CRO will provide instructions to investigators on how to introduce data in the eCRF when data collection starts; these instructions will also be briefly reminded to investigators every time they access the eCRF. During the

entire duration of the study, The CRO will provide technical support to investigators participating in the study.

Each investigator will be responsible for ensuring the accuracy of data entered in the eCRF as well as for completing all sections included in the eCRF. Each investigator commits to enter all data following their usual clinical practice.

The CRO will be responsible for supervising patients' recruitment through eCRF. During data collection period, standard monthly emails will be sent to investigators to inform about its progression, deal with any issues and remind investigators on their responsibilities. The CRO will guarantee database quality, compliance and accuracy of data introduced in the eCRF. The CRO will review the information entered through the web application weekly to guarantee data is being introduced correctly. If an inconsistency is detected during eCRF data review, the CRO will contact investigators via fax or email so that information can be clarified.

Investigators will guard original documents from each patient. All the information introduced in the eCRF will need to be traceable from original medical charts. Participating investigators from each site will keep a patient tracking sheet that will contain patients name together with assigned consecutive numbers and date of birth to allow identification. Investigators must also keep the original signed written informed consent from all patients included in the study.

When the CRO receives the completed questionnaires they will be handed to data entry department personnel that will introduce questionnaire answers in the study data base. Patients' questionnaires will be kept in the CRO office until statistical final report is completed. After that, they will be kept by the study sponsor.

## **10. Ethical considerations**

Investigators participating in the study will follow the principles described in the latest version of the Helsinki Declaration. Copies of the Helsinki Declaration and subsequent revisions will be supplied on request or can be obtained from the World Medical Association website (<http://www.wma.net/e/policy/17-c.html>). The study will follow the International Guidelines for Ethical Review of Epidemiological Studies (Council for the International Organizations of Medical Sciences-CIOMS-Ginebra, 2009) and local recommendations.

The study will be reviewed and approved by the appropriate Ethics Committee(s) according to their specific legal requirements. The study follows Spanish data protection laws; patient and data confidentiality will be respected.

The type of approvals required and the estimated time to receive approvals depends on requirements of the local ethical committees.

